The study population consists of all adult patients (age ≥ 18) having undergone laparoscopic anti-reflux surgery (Nomesco Classification of Surgical Procedures (NCSP) (45): KJBC01) from January 1, 2002 to December 31, 2013 in The Department of Surgery, Kolding Hospital, a part of Lillebaelt Hospital Denmark (n=557). Patients will be identified through Lillebaelt Hospital's Patient Administrative System. Day of surgery will be considered index date.

Date of follow-up will be the date, patient filled out quality of life questionnaires as described below. For patients deceased since index date, permission to include data from electronic patient records and registry-based data will be applied for from The Danish Patient Safety Authority.

All patients will be contacted by the existing Danish national digital communication system (e-Boks) and asked to participate in the study. Patients exempt from using the system, will be contacted by letter. Only patients providing informed consent will be included in the study.

Data sources

Data for the study will consist of electronic patient records, follow-up with patient-reported quality of life measurements and registry-based data.

Electronic patient records

From the electronic patient records, the following data will be identified: age (years), sex (male/female), body mass index (kg/m^2), alcohol consumption (drinks of 12g ethanol per week), tobacco use (current, former or never-smoker), ASA-score, Charlson Comorbidity Index (CCI) (46) and previous abdominal surgery (yes/no).

Preoperative endoscopically verified occurrence of hiatal hernia (yes/no), esophagitis (yes/no) will be included as well as, from 24-hour pH-measurement and esophageal manometry, reflux-index (%), symptom correlation (%) and presence of esophageal motility disorder (hypomotility, normal motility or hypermotility). Patients preoperative reflux symptoms defined as typical symptoms (yes/no), atypical symptoms (yes/no) and dysphagia (yes/no) are included as are surgical data included duration of surgery (minutes), type of fundoplication (270° Toupet/360° Nissen), Length of hospital stay (days), per- and postoperative complications registered within 30 days as defined by Clavien-Dindo (47).

Quality of life follow-up

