The Danish National Prescription Registry on use of anti-reflux medication (ATC: A02BA, A02BC, A02BX), anti-thrombotic treatment (ATC: B01A), non-steroid anti-inflammatory drugs (NSAID) (ATC: M01A) and selective serotonin reuptake inhibitors (SSRI) (ATC: N06AB) in a time period beginning two years before surgery and ending at end of follow-up. The Danish National Prescription Registry contains information on all sale of prescription drugs including date of sale, Anatomical Therapeutic Chemical Classification (ATC) code, civil registration number of buyer and package volume since 1994 (53).

Statistics Denmark on educational level at time of primary surgery (54) defined by ISCED (55), occupation status (employed/unemployed/retired) (56) and equivalent annual income in the year preceding primary surgery (57).

Primary outcome

Primary outcome of the study is treatment success or failure, with failure defined for each patient as at least one of the following statements being fulfilled:

1. Having undergone reoperation (NSCP: KJBC00-02, KJBW96-98, KJBB00-01, KJBB96-97) between index date and end of follow-up.
2. Having filled prescription of >60 DDD/year of PPI in any year between index date and end of follow-up.
3. Having no measure ≥ 3 on GERD-HRQL indicating symptoms being bothersome every day.
4. Having no measure ≥ 4 on Dysphagia Handicap index indicating symptoms being a moderate problem.

Date of failure will be defined as follows: In case of 1), date of failure will be date of reoperation. In case of 2), date of failure will be date of first prescription filled in the year, where >60 DDD of PPI are filled. In case of 3) or 4), date of failure will be end of follow-up.

Secondary outcomes

Secondary outcome will be 90-day mortality after primary surgery, rate of reoperation, use of PPI in DDD/year, use of PPI at follow-up (including indication and prescribing physician) and Quality of life defined by GERD_HRQL, Dysphagia Handicap Index.

Statistical analysis

Contingency tables

Contingency tables will be created listing:

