Cox regression will be performed with treatment success as dependent variable, time to end of follow-up (as defined above) and the following variables will be tested and included as independent variables where appropriate: Age (median), sex (male/female), body mass index (kg/m²), alcohol consumption (drinks of 12g ethanol per week), tobacco use (current, former or never-smoker), ASA-score, CCI, preoperative psychiatric diagnoses, use of anti-reflux medication (yes/no), NSAID (yes/no) and SSRI before surgery (yes/no) and previous abdominal surgery (yes/no), educational level at time of primary surgery (ISCED), occupation status (employed/unemployed/retired) and equivalent annual income in the year preceding primary surgery, typical symptoms (yes/no), atypical symptoms (yes/no) and dysphagia (yes/no), endoscopically verified occurrence of hiatal hernia (yes/no), esophagitis (yes/no), measures from 24-hour pH-measurement and esophageal manometry: reflux-index (%), symptom correlation (%) and presence of esophageal motility disorder (hypomotility, normal motility or hypermotility), type of fundoplication (270° Toupet/360° Nissen).

Clinical scoring system

Using results from the Cox regression and using the methods for validation described by Steyerberg et al (58), a clinical scoring system will be developed with the purpose of identifying probability of treatment success based on preoperative known variables.

Dataflow

Data collected from electronic patient records and patient-reported quality of life follow-up will be stored using RedCAP (REDCap 7.4.23, Vanderbilt University, Nashville, TN, USA) hosted by OPEN - Odense Patient Data Explorative Network, Department of Clinical Research, University of Southern Denmark and Odense University Hospital, Denmark. Data will be transferred to Statistics Denmark and merged with registry-data. All analysis will be performed using STATA15 (StataCorp, College Station, TX, USA) on the servers of Statistics Denmark.

Ethics and dissemination

The study has been approved and registered at Lillebaelt Hospital according to current Danish Law and has previously been approved by The Danish Data Protection Agency (Permission #17/1942). Generated datasets will be stored on the servers of Statistics Denmark in compliance with Danish and EU-regulations

on personal health data and will be anonymized after merging, so that the unique personal identifier is removed.

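### The Cox model takes treatment success timed to the questionnaire, but the plan dates only failures: event, stopping time, censoring and the end of follow-up for deceased patients must be stated

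*Combined protocol and SAP*

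**What the plan says.** The time origin is clear. Under Study population: "Day of surgery will be considered index date". The same section fixes the other end for patients who respond: "Date of follow-up will be the date, patient filled out quality of life questionnaires as described below".

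The Primary outcome section reads: "Primary outcome of the study is treatment success or failure, with failure defined for each patient" as meeting at least one of four criteria (reoperation, PPI prescriptions above a yearly threshold, a GERD-HRQL criterion, a Dysphagia Handicap Index criterion). It then dates failure. For reoperation: "In case of 1), date of failure will be date of reoperation". For PPI use: "date of failure will be date of first prescription filled in the year" that qualifies. Failures on the two questionnaire criteria are dated at end of follow-up. No date is given for success.

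The Cox regression section then says: "Cox regression will be performed with treatment success as dependent variable, time to end of follow-up (as defined above". It names no event and no censoring rule, and it does not mention the failure dates. The Clinical scoring system section uses the Cox results to derive a probability of success.

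On patients who have died, Study population says: "For patients deceased since index date, permission to include data from electronic patient records and registry-based data will be applied for". Ethics and dissemination repeats this intention. All-cause mortality is obtained from the Civil Registry (Registries section) but has no stated role in the model.

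**The concern.** A Cox model needs an event with an occurrence time, a stopping time for everyone else, and a rule for who is censored. Here the named dependent variable has no occurrence time, and the named time axis is not the one for which the plan defines dates. A failure on reoperation or PPI use can precede the questionnaire by years, so the choice of stopping time matters.

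Deceased patients return no questionnaire, so they have no end of follow-up. That date also closes the window in which reoperations and prescriptions count, so their outcome is undefined as well as their time.

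At stake are the coefficients of the primary-outcome model and the score built on them. Two analysts following different literal readings would obtain different scores from the same data.

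**Working it through.** The plan gives no event count, power or hazard ratio, so there is no figure to reproduce. The main check is to set the sections side by side.

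1. Origin: day of surgery (Study population). Stated.
2. Event: the Cox section names success; the Primary outcome section dates only failure. In conflict.
3. Stopping time for failures: the failure date (Primary outcome) or end of follow-up (Cox regression). In conflict.
4. Censoring: not stated anywhere.
5. End of follow-up: the questionnaire date for respondents; none for deceased patients.

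The literal wording leaves two readings. Under reading A, success is the event and everyone is timed to the questionnaire, so the failure dates are not used. Under reading B, success is the event and failures are censored at their failure date. Under B a patient who reaches the questionnaire without failing has the event on that day, so the model mainly describes length of follow-up.

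**Illustration of size (simulated; direction and order of magnitude only).** Inputs from the documents: 557 operated patients, surgery "from January 1, 2002 to December 31, 2013", and a 41.1% ten-year risk of long-term PPI use (Background). The yearly hazard is −ln(1 − 0.411)/10 = 0.053; the 5- and 15-year figures give −ln(1 − 0.294)/5 = 0.070 and −ln(1 − 0.566)/15 = 0.056. Assumptions not in the documents: 60% response (0.6 × 557 ≈ 334), uniform surgery dates, survey in mid-2018 ± 3 months, hazard 0.053 in the unexposed as a proxy for criteria 1 and 2, and one binary predictor with a true failure hazard ratio of 2 on those criteria and no change in prevalence over calendar time. A share q of 0, 15 or 25% of patients without such a failure fails on the questionnaire.

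| Model | Questionnaire failure unrelated to predictor (q 0, 15, 25%) | Also related, odds ratio 2 (q 15 / 25%) |
|---|---|---|
| A: success, timed to questionnaire | 0.60 | 0.53 / 0.47 |
| B: success, failures censored at failure | 1.00–1.01 | 0.87 / 0.80 |
| Failure at its defined date, all criteria | 2.01, 1.84, 1.77 | 1.96 / 1.92 |
| Failure, criteria 1 and 2 only | 1.99–2.03 | – |

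Failures on criteria 1 and 2 preceded the questionnaire by a median of about 6 years.

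A second simulation used n = 557, follow-up of 4–16 or 5–17 years, an average hazard of 0.055 and questionnaire failure of 0 or 15% in the reference group. It gave 0.58–0.71 for A, 0.85–1.01 for B and 1.96–2.03 for time to failure. A further possible coding, failure as event with everyone timed to the questionnaire, gave 1.55–1.70.

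**The case against.** The strongest reply is that the intended model is recoverable. A failure date is given for all four criteria, and the Cox model is its only evident use. Surgery as origin, failure date as event time and questionnaire date otherwise is the one reading that uses everything the plan defines. That stands as to intent. It does not settle the text: the parenthetical cross-reference attaches to end of follow-up, which is the questionnaire date, and the sentence points away from the intended model. Nor does it supply an end date for deceased patients.

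It can also be said that a success hazard ratio of 1.00 under reading B is the extreme case, since it needs questionnaire failures to be unrelated to a predictor that doubles other failures. That is correct, and it is why the range given is 0.8 to 1.0.

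Two stronger inferences should not be drawn.

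- A reader might infer that the planned model will produce false predictors. With nearly simultaneous questionnaires, time to end of follow-up is almost surgery date reversed. If a predictor's prevalence rose from 30 to 60% over the accrual years, a predictor with no effect would show a success hazard ratio of about 1.4 under both A and B. The documents do not show that any predictor drifted, so this is a possibility, and the severity does not rest on it.
- A reader might infer from 1.84 and 1.77 in the table that dating questionnaire failures late pulls a true hazard ratio of 2 towards 1. It does not. Those failures were simulated as unrelated to the predictor, so they dilute the composite. Giving them true onset dates produced 1.79 and 1.65, against 1.87 and 1.77 in the same check with the plan's dating. Likewise, the value near 2 on criteria 1 and 2 alone is built into the simulation and does not show that restricting to them removes a bias.

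**Conclusion.** The point holds and must be fixed. The Cox sentence conflicts with the outcome definition: followed literally it fits the wrong model to the primary outcome, and the score inherits it. Event, censoring rule and end of follow-up for deceased patients are all missing. Confidence is high on the conflict and the missing rules, which rest on the text alone.

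The size is illustrative. For a true failure hazard ratio of 2 without drift, reading A keeps the right direction but estimates a different quantity (about 0.5 to 0.6 for success), and reading B loses much or all of the effect (about 0.8 to 1.0). These values depend on the assumed survey timing, hazard, response and questionnaire-failure share. The size and sign of any error in the actual data are unknown.

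**What to change.** In the Cox regression section, state that the event is treatment failure, that time runs from the index date to the date of failure already defined under Primary outcome, and that patients without failure are censored at the questionnaire date. For deceased patients, end follow-up at the date of death and say whether death is a censoring or a competing event.

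Before the event is coded, reconcile criteria 3 and 4. They are worded as having no score at or above the threshold, which read literally counts patients without such symptoms as failures.

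The cost is a few sentences. Surgery, reoperation and prescription dates and mortality are already planned data.

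One limitation remains. Failures on criteria 3 or 4 alone stay dated at the questionnaire, because their true onset cannot be recovered. If predictors drift over calendar time, a modest bias can therefore persist. For a predictor with no effect, the simulated failure hazard ratio was 0.92 to 1.20 across the drift patterns tried (from 60 falling to 30%, up to 20 rising to 80%) with q of 15 or 25%. A sensitivity analysis on criteria 1 and 2 only, or one adjusted for year of surgery, is an optional check on this.

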Laparoscopic anti-reflux surgery is more effective than medical management with regard to short to medium length follow-up (12,34,35). Few studies provide long-term follow-up. After ten years, the benefits of surgery seem to decrease, but there is still a significant improvement in quality of life compared to preoperative measurements (36,39). Known causes of dissatisfaction are postoperative complication, redo-fundoplication and developing new bothersome symptoms such as gas-bloat and dysphagia combined with inadequate symptom relief (37,40).

Follow-up of randomized clinical trials have demonstrated, that anti-reflux surgery patients use acid suppressing drugs, primarily proton pump inhibitor (PPI) therapy at postoperative follow-up. Use have been considered minimal with <20% using PPI-therapy (35) and 27-44% using PPI at five-year follow-up (38). A recent register-based study (41), demonstrated a greater number of redeemed prescriptions of proton

pump inhibitor after primary anti-reflux surgery, than previously known. Five-, 10- and 15-year risks of long-term PPI use were 29.4%, 41.1% and 56.6%. However, this register-based study could not examine whether patients had objective recurrence of reflux disease and also did not examine indication for treatment as well as prescribing physician. From 2001 to 2011, 94.4% of PPI where prescribed in primary care (42) and it is unknown why post-fundoplication patients are prescribed PPI. It has previously been demonstrated, that the use of acid suppressing drugs after anti-reflux surgery does not necessarily correlate with abnormal acid exposure to the esophagus (43,44). In general, the use of PPI has increased rapidly in Denmark, rising 243% from 2001 to 2011 despite more restrictive guidelines and changes in reimbursement (42). As the majority of proton pump inhibitors are prescribed by general practitioners and not by the surgical centers, surgeons have very little knowledge of this aspect of life following anti-reflux surgery.

This study is part of the PhD project entitled: "Utilization, outcome and development of laparoscopic anti-reflux surgery" originating from the University of Southern Denmark (Protokol #: SDUSF-2016-115-(682)).

Methods and analysis

The study is a retrospective cohort study utilizing data from patient records and follow-up with patient-reported quality of life as well as registry-based data.

Study population

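### The scoring system draws on 24 candidate predictors in at most 557 patients, with no selection rule or shrinkage stated; unless corrected, its predicted probabilities would be too extreme

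*Combined protocol and SAP*

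**What the plan says.** The Cox regression section gives one sentence of model-building instruction: "the following variables will be tested and included as independent variables where appropriate". The list that follows begins "Age (median), sex (male/female), body mass index" and ends with type of fundoplication. It gives no p-value, information criterion, penalty, core set of predictors or limit on their number.

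The next section, Clinical scoring system, says that from these Cox results "a clinical scoring system will be developed with the purpose of identifying probability of treatment success based on preoperative known variables". For this it refers to a methods paper (reference 58), which the sentence cites for how to validate. The plan itself names no technique and does not mention shrinkage.

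The Study population section counts 557 eligible operations and adds: "Only patients providing informed consent will be included in the study". Deceased patients may enter by permission of an authority. The Primary outcome section makes failure a composite of four criteria, with "failure defined for each patient as at least one of the following statements being fulfilled". No expected number of failures is given. The nearest figure is in the Background, for another cohort: "Five-, 10- and 15-year risks of long-term PPI use were 29.4%, 41.1% and 56.6" per cent.

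**The concern.** The same patients would decide which predictors stay and what weight each receives. With many candidates and few events, the coefficients that survive tend to be those that chance has made large. A score built from them gives failure risks that are too high for patients it calls high-risk and too low for those it calls low-risk. Its C-index in the development data is also flattering.

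This matters because the stated aim is a score for choosing patients for surgery, and its output is an individual probability. Validation can measure the problem. It does not by itself change the coefficients that go into the score.

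**Working it through.** The plan states no sample size, event target or events-per-parameter figure, so there is nothing of its own to reproduce. The 557 is a count of operations.

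**Candidates.** The list holds 24 variables. Tobacco, occupation and motility have three levels each, which gives 24 + 3 = 27 degrees of freedom (df) as a minimum. The plan does not say how ASA score and education are coded. With three levels each, the total is 27 + 2 = 29. With three-level ASA and education in nine categories, it is 27 + 1 + 7 = 35. I use 29 below.

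**Events per parameter** = 557 × participation × failure rate / df. Participation is an assumption. The failure rate is borrowed from the Background figures for long-term PPI use, except for the assumed 70%.

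- 50% participation, 41.1%: 557 × 0.50 × 0.411 = 114 events; 114 / 29 = 3.9.
- 100% participation, 41.1%: 557 × 0.411 = 229 events; 229 / 29 = 7.9.
- Low end, 40% and 29.4%: 66 events; 2.3.
- High end, 100% and an assumed 70% composite rate: 390 events; 13.4.

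**Size needed for modest shrinkage.** The usual criterion is n = p / [(S − 1) ln(1 − R²/S)], where p is the candidate df, S the target shrinkage and R² the Cox-Snell value. R² is assumed here. With p = 29 and S = 0.90:

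- R² = 0.10: 29 / (0.1 × 0.1178) = about 2,463 patients.
- R² = 0.20: 29 / (0.1 × 0.2513) = about 1,154 patients.

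Turned round, 557 patients support about 6.6 df (557 × 0.01178) to 14.0 df (557 × 0.02513). Half that number, 279, supports about 3.3 to 7.0.

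**Simulation.** I simulated Cox models with 29 candidate df, 8 of them truly predictive, at a weak and a stronger signal (true C about 0.60 and 0.68). There were 100 replicates per setting, with performance measured in independent data. Since the plan names no selection rule, I assumed two: backward elimination at p<0.05 and univariable screening at p<0.05. Ranges are over rules and signals.

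| N | Events per parameter | Mean slope, selected model | Mean slope, full model, no shrinkage | Apparent minus new-patient C, selected |
|---|---|---|---|---|
| 279 | 3.9 | 0.42–0.75 | 0.28–0.55 | 0.04–0.07 |
| 390 | 7.5 | 0.55–0.81 | 0.43–0.68 | 0.02–0.05 |
| 557 | 7.8 | 0.58–0.87 | 0.46–0.75 | 0.03–0.04 |
| 557 | about 10.8 | 0.62–0.93 | 0.53–0.82 | 0.01–0.05 |
| 557 | about 14 | 0.73–0.90 | 0.61–0.81 | 0.02–0.03 |

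A slope of s means that the fitted log hazard ratios are too large by a factor of about 1/s: 1/0.42 = 2.4 at the bottom of the table and 1/0.93 = 1.1 at the top. Every mean slope is below 1, including where events per parameter exceed 10. In every setting the full model without shrinkage has a lower slope than the selected models.

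**Does penalisation help?** In separate runs (29 df, 10 true predictors, about 43% events, 40 replicates), ridge Cox with a cross-validated penalty gave mean slopes of 0.97 to 1.07. Single studies varied widely. At n = 334 the 10th to 90th percentiles were 0.63 to 1.57 with the weaker signal and 0.78 to 1.42 with the stronger.

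**The case against.** The best defence is that the plan relies on a recognised prediction-model paper, whose title covers development steps as well as validation. If the team follows it fully, selection may be handled inside resamples and coefficients may be shrunk. A reader might infer that reported discrimination is bound to be overstated, but the documents do not support that: a proper optimism correction would make the reported C-index honest. What remains is that the plan cites the paper for validation, commits to no technique, and says nothing on shrinkage.

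The figure of 4 to 8 events per parameter is not the plan's either. It needs an assumed participation rate and uses a cited PPI risk, whose definition of long-term use is not given, for a four-part composite. The plan's own PPI criterion is "Having filled prescription of >60 DDD/year of PPI in any year between index date and end of follow-up", which may capture a different share of patients. Criteria 3 and 4 read as though the absence of a high symptom score counts as failure, and the Cox section names success as the dependent variable. The event count therefore cannot be fixed. This objection stands, and it is why the figure is conditional and given with a range.

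The selection rules simulated are mine. The sentence could also cover checks for collinearity, missing data or proportional hazards, although choosing predictors on the data is the likelier reading. The slopes are illustrations of size, not forecasts.

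A reader might also infer that testing is the whole cause and that dropping it would cure the problem. The full-model column shows otherwise: too many parameters and no shrinkage matter at least as much.

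Finally, the label for age might suggest a split at the median. The same label appears in the descriptive table list, and the Electronic patient records section records age in years. It is a wording query, not evidence of dichotomisation.

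**Conclusion.** The concern holds in conditional form. The plan allows 24 candidates (27 to 35 df) to be chosen and weighted on the same data, in at most 557 patients less non-consenters, with no shrinkage stated. Unless this is corrected, the score's probabilities would be too extreme. The direction held in every setting examined. The size, slopes of about 0.4 to 0.9, depends on assumed selection rules and signal strength.

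About 4 to 8 events per parameter applies at 29 df, with 50 to 100% participation and 41.1% failure; wider assumptions give about 2 to 13. Optimistic discrimination depends on how validation is done: it follows if apparent performance is reported, and some would remain if resampling does not repeat the selection step. This should be settled before the score is built.

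**What to change.** Replace the selection sentence in the Cox regression section, and extend the Clinical scoring system section, to state that:

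1. A smaller predictor set is fixed on clinical grounds before outcome data are seen. The coding of each predictor is given, and continuous predictors, including age in years, stay continuous. The set is sized against an expected number of failures, which first requires criteria 3 and 4 to be reconciled.
2. The model is a penalised Cox model, or the pre-specified model with its coefficients multiplied by a bootstrap shrinkage factor. Dropping selection without this step is not enough.
3. If any data-driven selection is kept, its rule is written down and repeated inside every bootstrap sample.
4. The optimism-corrected C-index and calibration slope are reported.

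This needs no new data, only wording and some programming. Reported performance will look less favourable, and the score may hold more variables than a selected one. The penalty or shrinkage factor is itself imprecise in one study of this size, as the spread of single-study slopes shows, so its uncertainty should be reported too.

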Patients will be contacted as described above and asked to answer validated questionnaires regarding disease-specific quality of life (GERD-HRQL) (48) and dysphagia (Dysphagia Handicap Index) (49). Patients will also be asked if they are currently taking PPI (yes/no), in what dosage (never/when needed/once daily/twice daily), which symptoms have warranted PPI-use (reflux symptoms/dysphagia/gastritis/preemptive against peptic ulcer disease/other) and which physician prescribed the drug (general practitioner/surgeon/other doctor at hospital/other specialist in private practice)

Registries

All Danish inhabitant are issued with a civil registry number at birth or at date of moving to Denmark. The civil registry number are a unique personal identifier and is used across a variety of nationwide databases with regards to health, financial and educational data. Data from the following nationwide Danish registries will be included in the study:

The National Patient Registry (NPR) on re-operative surgery (NCSP: KJBC00-02, KJBW96-98, KJBB00-01, KJBB96-97) and endoscopy (NCSP: KUJD02-05, KJCA55) during follow-up). NPR contains records of all discharge diagnosis since 1977 and all outpatient diagnosis since 1994 (50,51). All performed procedures, including endoscopies and surgeries are also registered using NCSP.

The National Patient Registry of Psychiatry (NPR-PSYK) on psychiatric diagnoses (ICD-10: F01-F99) in a two-year period before primary surgery. NPR-PSYK is a sub-registry of NPR and specifically contains records of all psychiatric discharge and outpatient diagnosis from psychiatric departments since 1995 (50,51).

The Civil Registry on marital status, 90-day mortality after primary surgery and all-cause mortality during follow-up. The Danish Civil Registry maintains complete records of births, deaths, civic status and emigration status of the entire Danish population based on civil registration number (52).

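### The score takes an absolute probability of success from a Cox model with no rule for deaths and no horizon; if deaths are censored, the probability of failure is overstated

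*Combined protocol and SAP*

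**What the plan says.** - **Model.** Under Cox regression: "Cox regression will be performed with treatment success as dependent variable, time to end of follow-up (as defined above"). No rule for deaths and no competing-risk method is given.
- **Score.** The Cox results feed a clinical score "with the purpose of identifying probability of treatment success based on preoperative known variables". No time horizon is attached to that probability. Under Ethics and dissemination, the score is the subject of one of the two planned articles.
- **Deceased patients.** Under Study population: "For patients deceased since index date, permission to include data from electronic patient records and registry-based data will be applied for". Ethics and dissemination repeats the intention.
- **Mortality data.** Under Registries, the Civil Registry supplies "90-day mortality after primary surgery and all-cause mortality during follow-up".
- **Use of mortality.** Secondary outcomes begins: "Secondary outcome will be 90-day mortality after primary surgery, rate of reoperation, use of PPI in DDD/year". The operative contingency table also lists 90-day mortality. Later deaths appear in no outcome, table or model.
- **Failure.** The four criteria under Primary outcome are reoperation, PPI use, GERD-HRQL and Dysphagia Handicap Index. Death is not among them. For the two questionnaire criteria, "In case of 3) or 4), date of failure will be end of follow-up".
- **End of follow-up.** "Date of follow-up will be the date, patient filled out quality of life questionnaires as described below". A deceased patient has no such date.

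**The concern.** A hazard ratio and an absolute probability ask different things of a Cox model. Hazard ratios with deaths censored can be read as cause-specific effects. The survival function cannot be read as the chance a real patient faces: with deaths censored, it gives the probability of not failing if failure were the only possible event. A patient who dies without failing can no longer fail, so the proportion who actually fail is smaller than one minus that function.

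The score's product is the absolute probability, intended to guide selection for surgery. Age, ASA-score and CCI are candidate predictors and can be expected to relate to mortality as well, so the discrepancy need not be the same for all the patients the score has to separate. A date-of-death exit time alone does not remove it, because that is exactly what censoring at death does.

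**Working it through.** The plan states no predicted probability, event count or mortality rate, so there is no figure to reproduce. The check compares the two candidate probabilities under stated assumptions.

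**Inputs**
- From the Background: risks of long-term PPI use of 29.4% at 5 years and 41.1% at 10 years, used as a stand-in for net failure.
- Assumed: 10-year mortality D of 5, 10, 20 or 30%, with a constant death hazard.

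**Hazards per year**
- Failure, years 0-5: h1 = -ln(0.706)/5 = 0.0696.
- Failure, years 5-10: h2 = -ln(0.589/0.706)/5 = 0.0362.
- Death: d = -ln(1 - D)/10. For D = 30%, d = 0.0357.

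**Formulas**
- Deaths censored: F = 1 - exp(-5·h1 - 5·h2) = 41.1% at 10 years, whatever D is.
- Cumulative incidence: for each 5-year interval, add S·[h/(h + d)]·[1 - exp(-5(h + d))], where S is the probability of being alive without failure at the start of the interval.

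**Worked case, D = 30%**
- Years 0-5: (0.0696/0.1053) × (1 - 0.5907) = 0.271, leaving S = 0.5907.
- Years 5-10: 0.5907 × (0.0362/0.0719) × (1 - 0.6980) = 0.090.
- Sum: 36.1%, against 41.1% with deaths censored, a difference of 5.0 points.

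| Assumed 10-year mortality | Cumulative incidence, 5 y (censored: 29.4%) | Excess | Cumulative incidence, 10 y (censored: 41.1%) | Excess |
|---|---|---|---|---|
| 5% | 29.0% | 0.4 | 40.3% | 0.8 |
| 10% | 28.7% | 0.7 | 39.5% | 1.6 |
| 20% | 27.9% | 1.5 | 37.8% | 3.3 |
| 30% | 27.1% | 2.3 | 36.1% | 5.0 |

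**Sensitivity to the failure hazard.** With 0.3 times the failure hazard, the 10-year excess at 20% mortality falls from 3.3 to 1.3 points (14.7% against 13.4%).

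**Dependence on the unstated rule.** A simulation of 400,000 patients included a group with 30% 10-year mortality. In that group the true cumulative incidence of failure at 10 years was 35.9%. Censoring deaths gave 41.0%, dropping deceased patients gave 41.2%, and keeping deceased non-failures at risk to their administrative end date gave 35.9%.

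**Consequence for success at 10 years.** Cox success with deaths censored is 100 - 41.1 = 58.9%. Not failed, dead or alive, is 100 minus the cumulative incidence. Alive without failure is 58.9% × (1 - D).

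| Assumed 10-year mortality | Not failed, dead or alive | Cox error | Alive without failure | Cox error |
|---|---|---|---|---|
| 5% | 59.7% | -0.8 | 56.0% | +2.9 |
| 10% | 60.5% | -1.6 | 53.0% | +5.9 |
| 20% | 62.2% | -3.3 | 47.1% | +11.8 |
| 30% | 63.9% | -5.0 | 41.2% | +17.7 |

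The sign of the error in predicted success is therefore set by a definition that the plan does not give.

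**The case against.** **The plan does not say that deaths are censored.** This stands. A reader might infer that it does, because that is the usual default, but the text is silent and end of follow-up is undefined for the deceased. As the simulation shows, one way of filling that gap produces no overstatement of failure. The criticism is of an unspecified rule whose likeliest reading has this consequence.

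**The direction for success is not fixed.** This also stands. A reader might conclude that surgery would look less successful in older and sicker patients than it was. That holds only if a death without failure counts as not failed. If success means alive without failure, the error has the opposite sign.

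**The size is borrowed.** Largely right. The cited risks concern long-term PPI use. They cover one of four criteria, are not shown to match the plan's threshold of more than 60 DDD in any year, and are not shown to be net risks. A single constant hazard would fit them poorly: 41.1% at 10 years implies 1 - √0.589 = 23.3% at 5 years, against the cited 29.4%. Hence the piecewise hazards. Assigning a given number of points to young or old patients is not supported either: the documents give no age or mortality data, and the gap also depends on each group's failure hazard.

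**The net probability may be the intended target.** The chance that the repair holds while the patient lives is a defensible quantity for selecting patients. But the plan would have to say so, and it does not.

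**Sampling error is comparable.** For an assumed subgroup of 100 of the 557 patients, the standard error of a 40% risk is √(0.4 × 0.6/100) = 4.9 points. This limits how closely calibration can be checked. It does not excuse a systematic error that can be avoided with mortality data already requested.

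**The questionnaire criteria cannot be observed in the deceased.** Correct. A competing-risk model cannot simply be added for the whole composite, and the fix has to allow for this.

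**Conclusion.** The point holds as a gap with a calculable consequence. The plan promises an absolute probability, provides for deceased patients and retrieves their mortality, but gives no rule for deaths, no horizon and no use of deaths beyond 90 days. If deaths are censored, failure is overstated whenever patients die before failing. That direction does not depend on the assumed figures.

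The size does. It is below 1 point at 10 years if 10-year mortality is about 5% and about 5 points if it is 30%; over the same range it stays at or below 2.3 points at 5 years. These figures rest on assumed mortality, on cited PPI risks standing in for failure, and on failure being the modelled event. The last fits the date-of-failure rules, although the Cox section names success as the dependent variable.

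The documents do not support a claim that the score is biased against older or sicker candidates, or that the associations from the Cox model are invalid. The matter should be settled before the score is developed.

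**What to change.** Keep the Cox model for associations, read as cause-specific hazard ratios. For the score:

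1. State a fixed prediction horizon.
2. Define the exit date of deceased patients as the date of death.
3. State whether death without failure counts as success, and treat it as a competing event.
4. Take the predicted probability from a cumulative incidence, using cause-specific Cox models for failure and for death combined, or a Fine-Gray model.
5. Check calibration against the observed cumulative incidence at the stated horizon.
6. Either apply this prediction to the registry-dated components, reoperation and PPI use, or state explicitly that questionnaire failures are unobserved in the deceased and are dated at the questionnaire in everyone else.

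**Cost.** One added model, a paragraph of analysis text and a slightly more complex score. The mortality data are already requested. If the score is confined to the registry-dated components, it predicts a narrower outcome than the primary one, and the article should say so.
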